9.2.2. Exclusion Criteria

Patients meeting any of the following criteria will not be included in the study:

- Had medical claims indicating a diagnosis or procedure of rheumatic mitral valvular heart disease, heart valve replacement/transplant, venous thromboembolism, or transient AF 6 months prior to or on the index date.
- Had hip/knee replacement surgery within 6 weeks prior to or on the index date.
- Were pregnant during the study period.
- Had an OAC prescription during the 6 months pre-index date.
- Had follow-up time equal to 0 days.
- Had more than one OAC on the index date.

Flag: A flag will be created to evaluate the mechanical heart valve/mitral stenosis during the 6 months prior to or on the index date using narrow definition.

All codes for the selection criteria are detailed in Appendix [Table 4](#).

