17. ANNEX 2. ADDITIONAL INFORMATION

17.1. Appendix

Table 4. Exclusion Criteria

Diagnosis	ICD-9 Code	ICD-10 Code
Valvular Heart Disease	394.0, 394.1, 394.2, 394.9, 396.0, 396.1, 396.8, 396.9, 424.0, 745.xx	I050, I051, I052, I058, I059, I080, I088, I089, I340, I341, I342, I348, I349, Q213, Z952, Z953, Z954
Mechanical Heart Valve/ Mitral Stenosis (narrow definition)	ICD-9-CM: 996.02, 996.71, 394.0, 394.2, 396.0, 396.1, 746.5 ICD-9 procedure: 35.20, 35.22, 35.24, 36.23, 35.97 CPT: 33405, 92987, 33427, 33426, 33425, 33422, 33420, 33430	ICD- 10 diagnosis codes: T82.01XA, T82.02XA, T82.03XA, T82.09XA, T82.817A- T82.897A, T82.9XXA, I05.0, I05.2, I08.0, Q23.2 ICD-10 Procedure Codes: 02RF07Z, 02RF08Z, 02RF0JZ, 02RF0KZ, 02RF37H, 02RF37Z, 02RF38H, 02RF38Z, 02RF3JH, 02RF3JZ, 02RF3KH, 02RF3KZ, 02RF47Z, 02RF48Z, 02RF4JZ, 02RF4KZ, 02RG07Z, 02RG08Z, 02RG0JZ, 02RG0KZ, 02RG37H, 02RG37Z, 02RG38H, 02RG38Z, 02RG3JH, 02RG3JZ, 02RG3KH, 02RG3KZ, 02RG47Z, 02RG48Z, 02RG4JZ, 02RG4KZ, 02RH07Z, 02RH08Z, 02RH0JZ, 02RH0KZ, 02RH37H, 02RH37Z, 02RH38H, 02RH38Z, 02RH3JH, 02RH3JZ, 02RH3KH, 02RH3KZ, 02RH47Z, 02RH48Z, 02RH4JZ, 02RH4KZ, 02RJ07Z, 02RJ08Z, 02RJ0JZ, 02RJ0KZ, 02RJ47Z, 02RJ48Z, 02RJ4JZ, 02RJ4KZ, 02UG3JZ, X2RF03Z, X2RF33Z, X2RF43Z

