VTE	DVT: 451-453, 671.3, 671.4, 671.9; or PE: 415.1, 673.2, 673.8	I2601, I2602, I2609, I2690, I2692, I2699, I8010, I8011, I8012, I8013, I80201, I80202, I80203, I80209, I80211, I80212, I80213, I80219, I80221, I80222, I80223, I80229, I80231, I80232, I80233, I80239, I80291, I80292, I80293, I80299, I803, I808, I809, I81, I820, I821, I82210, I82211, I82220, I82221, I82290, I82291, I823, I82401, I82402, I82403, I82409, I82411, I82412, I82413, I82419, I82421, I82422, I82423, I82429, I82431, I82432, I82433, I82439, I82441, I82442, I82443, I82449, I82491, I82492, I82493, I82499, I824Y1, I824Y2, I824Y3, I824Y9, I824Z1, I824Z2, I824Z3, I824Z9, I82501, I82502, I82503, I82509, I82511, I82512, I82513, I82519, I82521, I82522, I82523, I82529, I82531, I82532, I82533, I82539, I82541, I82542, I82543, I82549, I82591, I82592, I82593, I82599, I825Y1, I825Y2, I825Y3, I825Y9, I825Z1, I825Z2, I825Z3, I825Z9, I82601, I82602, I82603, I82609, I82621, I82622, I82623, I82629, I82701, I82702, I82703, I82709, I82711, I82712, I82713, I82719, I82721, I82722, I82723, I82729, I82890, I82891, I8290, I8291, I82A11, I82A12, I82A13, I82A19, I82A21, I82A22, I82A23, I82A29, I82B11, I82B12, I82B13, I82B19, I82B21, I82B22, I82B23, I82B29, I82C11, I82C12, I82C13, I82C19, I82C21, I82C22, I82C23, I82C29, O871, O88211, O88212, O88213, O88219, O8822,

Diagnosis	ICD-9 Code	ICD-10 Code
		O8823, T82817A, T82818A
Transient AF	Pericarditis: 006.8, 017.9, 036.41, 074.21, 093.81, 098.83, 115.93, 390, 391, 392.0, 393, 411.0, 420.90, 420.91, 420.99, 423.0, 423.1, 423.2, 423.8, 423.9; Hyperthyroidism and Thyrotoxicity: 242.0, 242.1, 242.2, 242.3, 242.4, 242.8, 242.9	A1884, A3953, A5206, A5483, B3323, E0500, E0501, E0510, E0511, E0520, E0521, E0530, E0531, E0540, E0541, E0580, E0581, E0590, E0591, I010, I011, I012, I018, I019, I020, I092, I241, I300, I301, I308, I309, I310, I311, I312, I313, I318, I319, I32, Z952, Z953, Z954, I300, I301, I308, I309

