Valve Replacement Procedure	ICD-9-PCS/HCPCS Codes: 35.05-35.09, 35.20-35.28, 35.97	ICD-10-PCS Codes: 02RF07Z, 02RF08Z, 02RF0JZ, 02RF0KZ, 02RF37H, 02RF37Z, 02RF38H, 02RF38Z, 02RF3JH, 02RF3JZ, 02RF3KH, 02RF3KZ, 02RF47Z, 02RF48Z, 02RF4JZ, 02RF4KZ, 02RG07Z, 02RG08Z, 02RG0JZ, 02RG0KZ, 02RG37H, 02RG37Z, 02RG38H, 02RG38Z, 02RG3JH, 02RG3JZ, 02RG3KH, 02RG3KZ, 02RG47Z, 02RG48Z, 02RG4JZ, 02RG4KZ, 02RH07Z, 02RH08Z, 02RH0JZ, 02RH0KZ, 02RH37H, 02RH37Z, 02RH38H, 02RH38Z, 02RH3JH, 02RH3JZ, 02RH3KH, 02RH3KZ, 02RH47Z, 02RH48Z, 02RH4JZ, 02RH4KZ, 02RJ07Z, 02RJ08Z, 02RJ0JZ, 02RJ0KZ, 02RJ47Z, 02RJ48Z, 02RJ4JZ, 02RJ4KZ, 02UG3JZ, X2RF032, X2RF332, X2RF432
Hip/knee replacement surgery	ICD-9-PCS/HCPCS Codes: 81.40, 81.51, 81.52, 81.53, 81.54, 81.55	ICD-10-PCS Codes: 0SQ90ZZ, 0SQ93ZZ, 0SQ94ZZ, 0SQ9XZZ, 0SQB0ZZ, 0SQB3ZZ, 0SQB4ZZ, 0SQBXZZ, 0SR90J9, 0SR90JA, 0SR90JZ, 0SRB0J9, 0SRB0JA, 0SRB0JZ, 0SRA009, 0SRA00A, 0SRA00Z, 0SRA019, 0SRA01A, 0SRA01Z, 0SRA039, 0SRA03A, 0SRA03Z, 0SRA07Z, 0SRA0J9, 0SRA0JA, 0SRA0JZ, 0SRA0KZ, 0SRE009, 0SRE00A, 0SRE00Z, 0SRE019, 0SRE01A, 0SRE01Z, 0SRE039, 0SRE03A, 0SRE03Z, 0SRE07Z, 0SRE0J9, 0SRE0JA, 0SRE0JZ, 0SRE0KZ, 0SRR019, 0SRR01A, 0SRR01Z, 0SRR039, 0SRR03A, 0SRR03Z, 0SRR07Z, 0SRR0J9, 0SRR0JA, 0SRR0JZ, 0SRR0KZ, 0SRS019, 0SRS01A, 0SRS01Z, 0SRS039, 0SRS03A, 0SRS03Z, 0SRS07Z, 0SRS0J9, 0SRS0JA, 0SRS0JZ, 0SRS0KZ, 0SW90JZ, 0SW93JZ, 0SW94JZ, 0SWA0JZ, 0SWA3JZ, 0SWA4JZ, 0SWB0JZ, 0SWB3JZ, 0SWB4JZ, 0SWE0JZ, 0SWE3JZ, 0SWE4JZ, 0SWR0JZ, 0SWR3JZ, 0SWR4JZ, 0SWS0JZ, 0SWS3JZ, 0SWS4JZ, 0SRC07Z, 0SRC0JZ, 0SRC0KZ, 0SRC0LZ, 0SRD07Z, 0SRD0JZ, 0SRD0KZ, 0SRD0LZ, 0SRT07Z, 0SRT0JZ, 0SRT0KZ, 0SRU07Z, 0SRU0JZ, 0SRU0KZ, 0SRV07Z, 0SRV0JZ, 0SRV0KZ, 0SRW07Z, 0SRW0JZ, 0SRW0KZ, 0SWC0JC, 0SWC0JZ, 0SWC3JC, 0SWC3JZ, 0SWC4JC, 0SWC4JZ, 0SWD0JC, 0SWD0JZ, 0SWD3JC, 0SWD3JZ, 0SWD4JC, 0SWD4JZ, 0SWT0JZ, 0SWT3JZ, 0SWT4JZ, 0SWU0JZ,

Diagnosis	ICD-9 Code	ICD-10 Code
		0SWU3JZ, 0SWU4JZ, 0SWV0JZ, 0SWV3JZ, 0SWV4JZ, 0SWW0JZ, 0SWW3JZ, 0SWW4JZ

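### Table 4 codes prior valve replacement as a diagnosis only in ICD-10, so a patient known only by a valve-status code is excluded in ICD-10 data but admitted in ICD-9 data

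*Combined protocol and SAP*

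**What the plan says.** The valve exclusion in section 9.2.2 covers both diagnoses and procedures: "Had medical claims indicating a diagnosis or procedure of rheumatic mitral valvular heart disease, heart valve replacement/transplant". It looks back six months from the index date and refers to Appendix Table 4 for all selection codes.

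Table 4 has three exclusion rows that bear on this:

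- **Valvular Heart Disease.** The ICD-9 column reads in full "394.0, 394.1, 394.2, 394.9, 396.0, 396.1, 396.8, 396.9, 424.0, 745.xx". The ICD-10 column ends "I340, I341, I342, I348, I349, Q213, Z952, Z953, Z954".
- **Transient AF.** The ICD-10 column repeats the same three Z codes: "I318, I319, I32, Z952, Z953, Z954, I300, I301, I308, I309". The ICD-9 column holds a pericarditis list and "Hyperthyroidism and Thyrotoxicity: 242.0, 242.1, 242.2, 242.3, 242.4, 242.8, 242.9".
- **Valve Replacement Procedure.** The ICD-9 column is "ICD-9-PCS/HCPCS Codes: 35.05-35.09, 35.20-35.28, 35.97". The ICD-10 column is likewise procedure codes only.

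A fourth row, the narrow definition of mechanical valve or mitral stenosis, is described in section 9.2.2 as a flag and is not among the exclusion bullets.

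**The concern.** The study is about non-valvular AF, and section 9.2.2 means to remove patients with a replaced valve. In claims data a valve implanted long before the index date does not appear as an operation inside a six-month window. It appears, if at all, as a status code recorded at a later visit. The ICD-10 lists use that route and the ICD-9 lists do not, so whether such a patient is eligible depends on which coding system was in force during the look-back.

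Two consequences follow. The early and late parts of the cohort are selected by different rules. And if the patients who slip in are unevenly divided between apixaban and warfarin, the primary comparison includes ineligible patients in unequal proportions, with no valve-prosthesis variable among the Table 1 or Table 11 covariates to adjust for it.

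**Working it through.** The plan gives no figure to reproduce here. The check is a comparison of the code lists, followed by a calendar count.

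**1. Valve-status codes, row by row (Table 4)**

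| Row | Role in 9.2.2 | ICD-9 content | ICD-10 content | Status codes, ICD-9 / ICD-10 |
|---|---|---|---|---|
| Valvular Heart Disease | Exclusion | 394.x, 396.x, 424.0, 745.xx | Native-valve codes, Q213, Z952–Z954 | 0 / 3 |
| Transient AF | Exclusion | Pericarditis, thyroid | Pericarditis, thyroid, Z952–Z954 | 0 / 3 (same three) |
| Valve Replacement Procedure | Exclusion | Procedures | Procedures | 0 / 0 |
| Narrow mechanical valve / mitral stenosis | Flag | 996.02, 996.71, 394.x, 396.x, 746.5, procedures | T82, I05, I08 and Q23.2 codes, procedures | 0 / 0 |

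Distinct valve-status codes in the exclusion rows: 0 in ICD-9, 3 in ICD-10. The only V codes anywhere in Table 4 are in the pregnancy row. Table 4 prints no descriptions for Z952–Z954. Reading them as replaced-valve status is standard coding knowledge and fits the row they sit in.

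**2. What the lists do to particular patients**

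Take a patient whose valve was replaced well before the look-back, or as stated:

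| Evidence in the six-month window | ICD-9 data | ICD-10 data |
|---|---|---|
| Status code only | Admitted | Excluded |
| Status code plus a valve-disease code listed in that system (e.g. 424.0 in ICD-9) | Excluded | Excluded |
| Replacement procedure in the window | Excluded | Excluded |
| Status code plus an OAC prescription | Excluded (washout) | Excluded |
| No valve code or procedure, no OAC | Admitted | Admitted |

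Only the first line differs between the systems. That is the whole of the gap.

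**3. How much of the identification period is affected**

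Inputs: identification period 1 July 2013 to 31 December 2017 and a six-month baseline (section 9.1.1). Assumption: coding changed on 1 October 2015.

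- Length of period: 6 + 4 × 12 = 54 months, or 184 + 365 + 365 + 366 + 365 = 1,645 days.
- Index dates before the change: July 2013 to September 2015 = 6 + 12 + 9 = 27 months, or 184 + 365 + 273 = 822 days. 27/54 = 50%. All of these have an all-ICD-9 look-back.
- Mixed look-back: index October 2015 to March 2016 = 6 months, 6/54 = 11%. The exclusion works here only if the status code was recorded after the change.
- All-ICD-10 look-back: April 2016 to December 2017 = 9 + 12 = 21 months, 21/54 = 39%.
- Check: 27 + 6 + 21 = 54.
- If the change came six months earlier or later, the share of index dates before it is 21/54 = 39% or 33/54 = 61%.

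**4. The same row is unequal in the other direction**

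ICD-9 excludes the whole 745.xx family, while ICD-10 lists only Q213. The text of 9.2.2 names neither.

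**5. Does the plan use ICD-9 status codes elsewhere?**

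Yes. Table 9 pairs V45.86 with Z98.84 for bariatric surgery status. This shows that such codes are within the plan's method, though the pairing is not uniform: Tables 5 and 6 carry V12.54 without Z8673, while Table 7 carries both.

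**The case against.** The strongest reply is that the gap is narrow and already thinned by other rules.

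- **Other ICD-9 codes exclude too.** A reader might infer that in ICD-9 data only a replacement operation inside the window removes a patient. The documents do not support that: 394.x, 396.x, 424.0 and 745.xx in the window also exclude. This stands, and it limits the point to patients with a status code and nothing else.
- **The OAC washout.** Section 9.2.2 removes anyone with an OAC prescription in the prior six months, which takes out prosthesis patients on continuous warfarin. This also stands. Lapsed users, and prosthesis patients not on an OAC in that window, remain.
- **No count is available.** A reader might apply an assumed prosthesis prevalence to half of the roughly 56,000 patients in section 9.5. The documents give no prevalence. The 56,000 are patients with a reported BMI or weight, not the obese apixaban and warfarin cohorts alone, and such a product would ignore overlap with the two rules above.
- **Year of index could be adjusted for.** It is a Table 1 variable, but section 9.7.1 does not commit it to the propensity model, and adjusting for it would not remove ineligible patients.
- **The narrow flag could be used as an exclusion.** It would not close the gap, since its ICD-9 list has no status code either.
- **The Z codes under Transient AF.** Their repetition there looks misplaced, but both rows exclude over the same window, so moving them changes no one's eligibility. That is cosmetic.

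None of these replies supplies the missing ICD-9 diagnosis route.

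**Conclusion.** The point holds as a code-list inconsistency. Section 9.2.2 states one exclusion, and Table 4 implements its diagnosis part for valve replacement in ICD-10 only. The patients affected are those with an older prosthesis whose sole valve evidence in the look-back is a status code and who have no OAC prescription in that period. On the assumed changeover date, index dates in 27 of 54 months are fully exposed and 6 more partly.

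The number of patients cannot be derived from the documents, and the effect on the hazard ratio is probably small; that is a judgment, not a calculation. A reader might go further and conclude that the apixaban versus warfarin comparison is confounded. The documents do not establish that. Bias would arise if these patients are weighted toward warfarin, which the documents do not say, or if ICD-9-era initiators generally are. The second is plausible, because section 7 describes DOACs as increasingly preferred over warfarin in the years since approval, but the cohort mix by year is not given.

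The 745.xx versus Q213 mismatch is real but secondary.

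**What to change.** In Table 4:

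1. Add the ICD-9 counterparts of Z952–Z954 to the valve exclusion. The candidates are V42.2 and V43.3, to be confirmed by the coding team.
2. Make the 745.xx and Q213 entries equivalent in both systems, either by dropping both or by listing the full ICD-10 counterpart, and say in 9.2.2 if these conditions are meant to exclude.
3. Report attrition for each valve row by coding era (all-ICD-9, mixed and all-ICD-10 look-back). This fits the attrition check already in section 9.8 and would show how many patients are involved.

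The cost is a code-list edit before the cohort is built and a somewhat smaller ICD-9-era cohort. If the cohort has already been built, the selection step and everything after it would have to be rerun.

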9. RESEARCH METHODS

9.1. Study Design

9.1.1. Key Index Period Definitions

[figure not shown]
- **Study Period:** The study period will range from January 1, 2013 through December 31, 2017.
- **Patient Identification Period:** The identification period will range from July 1, 2013 until December 31, 2017, allowing for a 6-month baseline period prior to the index date.
- **Baseline Period:** The baseline period will be 6 months prior to, and on, the index date.
- **Follow-up Period:** The follow-up period will be defined as the time period between the day after the index date and end of study period (December 31, 2017). Patients will be followed from the day after the index date to 30 days after the date of discontinuation, switch, death, end of study period, or end of continuous medical enrollment (Parts A & B), whichever is earlier.

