9.7.2. Analysis Plan for Secondary CCI [REDACTED]

Any further comparisons or sub-group analysis will be assessed and conducted based on feasibility analysis to ensure adequate sample size through power calculation.

CCI [REDACTED]

[REDACTED]

[REDACTED]

CCI [REDACTED]

[REDACTED]

Sensitivity Analysis: Propensity Score Matching

The propensity score matching (PSM) technique will be used to control for potential confounders when comparing the cohorts.³⁷ Covariates to be included in the logistic regression model may include the following variables: age, geographic region, Charlson comorbidity index score, comorbidities, and other clinical characteristics. The final list of

variables to be used in the model will be discussed and determined during analysis development, after reviewing the pre-matched descriptive tables. Each subject in the reference cohort will be matched to a subject in the comparator cohort with the closest propensity score. The nearest neighbor method without replacement and with a caliper of 0.01 will be used to select the matched samples. The balance of covariates between treatment groups will be determined using the absolute standardized difference of the mean ≤ 0.10 .

After PSM, no significant differences are expected among all pre-index measures between the patient cohorts. PSM with a different ratio (1:2 or 1:3) can also be considered if the matched sample size using a ratio of 1:1 is too small.

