Stroke	2	V12.54, 433-436	I6300, I63011, I63012, I63013, I63019, I6302, I63031, I63032, I63033, I63039, I6309, I6310, I63111, I63112, I63113, I63119, I6312, I63131, I63132, I63133, I63139, I6319, I6320, I63211, I63212, I63213, I63219, I6322, I63231, I63232, I63233, I63239, I6329, I6330, I63311, I63312, I63313, I63319, I63321, I63322, I63323, I63329, I63331, I63332, I63333, I63339, I63341, I63342, I63343, I63349, I6339, I6340, I63411, I63412, I63413, I63419, I63421, I63422, I63423, I63429, I63431, I63432, I63433, I63439, I63441, I63442, I63443, I63449, I6349, I6350, I63511, I63512, I63513, I63519, I63521, I63522, I63523, I63529, I63531, I63532, I63533, I63539, I63541, I63542, I63543, I63549, I6359, I636, I638, I639, I6501, I6502, I6503, I6509, I651, I6521, I6522, I6523, I6529, I658, I659, I6601, I6602, I6603, I6609, I6611, I6612, I6613, I6619, I6621, I6622, I6623, I6629, I663, I668, I669

Table 6. CHADS₂-VASc Score

CHA ₂ DS ₂ –VASc	Point	ICD-9 Codes	ICD-10 Codes
Congestive Heart Failure	1	402.x1, 404.x1, 404.x3, 428.xx	I0981, I110, I132, I501, I5020, I5021, I5022, I5023, I5030, I5031, I5032, I5033, I5040, I5041, I5042, I5043, I509
Hypertension	1	401.xx-405.xx	I10, I110, I119, I120, I129, I130, I1310, I1311, I132, I150, I151, I152, I158, I159, I160, I161, I169, N262
Age ≥75 years	2	-	-
Diabetes mellitus	1	250, 357.2, 362.0, 366.41	E08311, E08319, E083211, E083212, E083213, E083219, E083291, E083292, E083293, E083299, E083311, E083312, E083313, E083319, E083391, E083392, E083393, E083399, E083411, E083412, E083413, E083419, E083491, E083492, E083493, E083499, E083511, E083512, E083513, E083519, E083521, E083522, E083523, E083529, E083531, E083532, E083533, E083539, E083541, E083542, E083543, E083549, E083551, E083552, E083553, E083559, E083591, E083592, E083593, E083599, E0836, E0840, E0842, E09311, E09319, E093211, E093212, E093213, E093219, E093291, E093292, E093293, E093299, E093311, E093312, E093313, E093319, E093391, E093392, E093393, E093399, E093411, E093412, E093413, E093419, E093491, E093492, E093493, E093499, E093511, E093512, E093513, E093519, E093521, E093522, E093523, E093529, E093531, E093532, E093533, E093539, E093541, E093542, E093543, E093549, E093551, E093552, E093553, E093559, E093591, E093592, E093593, E093599, E0936, E0940, E0942, E1010, E1011, E1021, E1022, E1029, E10311, E10319, E103211, E103212, E103213, E103219, E103291, E103292, E103293, E103299, E103311, E103312, E103313, E103319, E103391, E103392,

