Stroke (non-hemorrhagic only & transient ischemic attack)	2	V12.54, 433.xx-436.xx	I6300, I63011, I63012, I63013, I63019, I6302, I63031, I63032, I63033, I63039, I6309, I6310, I63111, I63112, I63113, I63119, I6312, I63131, I63132, I63133, I63139, I6319, I6320, I63211, I63212, I63213, I63219, I6322, I63231, I63232, I63233, I63239, I6329, I6330, I63311, I63312, I63313, I63319, I63321, I63322, I63323, I63329, I63331, I63332, I63333, I63339, I63341, I63342, I63343, I63349, I6339, I6340, I63411, I63412, I63413, I63419, I63421, I63422, I63423, I63429, I63431, I63432, I63433, I63439, I63441, I63442, I63443, I63449, I6349, I6350, I63511, I63512, I63513, I63519, I63521, I63522, I63523, I63529, I63531, I63532, I63533, I63539, I63541, I63542, I63543, I63549, I6359, I636, I638, I639, I6501, I6502, I6503, I6509, I651, I6521, I6522, I6523, I6529, I658, I659, I6601, I6602, I6603, I6609, I6611, I6612, I6613, I6619, I6621, I6622, I6623, I6629, I663, I668, I669
Vascular Disease (myocardial infarction, peripheral arterial disease, aortic	1	410.xx, 412, 440.xx, 441.xx, 442.xx, 443.xx, 444.2x, 445.0x	I200, I2101, I2102, I2109, I2111, I2119, I2121, I2129, I213, I214, I220, I221, I222, I228, I229, I240, I241, I248, I249, I25110, I252, I25700, I25710, I25720, I25730, I25750,

CHA2DS ₂ –VASc	Point	ICD-9 Codes	ICD-10 Codes

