Hypertension	1 point	401.xx-405.xx	I10, I110, I119, I120, I129, I130, I1310, I1311, I132, I150, I151, I152, I158, I159, I160, I161, I169, N262
Abnormal kidney and/or liver function:	1 point each	Kidney: 580.xx-589.xx	B520, E0821, E0822, E0829, E0921, E0922, E0929, M3214, M3215, M3504, N000, N001, N002, N003, N004, N005, N006, N007, N008, N009, N010, N011, N012, N013, N014, N015, N016, N017, N018, N019, N020, N021, N022, N023, N024, N025, N026, N027, N030, N031, N032, N033, N034, N035, N036, N037, N038, N039, N040, N041, N042, N043, N044, N045, N046, N047, N048, N049, N050, N051, N052, N053, N054, N055, N056, N057, N058, N059, N060, N061, N062, N063, N064, N065, N066, N067, N068, N069, N070, N071, N072, N073, N074, N075, N076, N077, N078, N079, N08, N140, N141, N142, N143, N144, N150, N158, N159, N16, N170, N171, N172, N178, N179, N181, N182, N183, N184, N185, N186, N189, N19, N250, N251, N2581, N2589, N259, N261, N269, N270, N271, N279
Age ≥75 years	2	Liver: 570.xx-573.xx	B251, K700, K7010, K7011, K702, K7030, K7031, K7040, K7041, K709, K710, K7110, K7111, K712, K713, K714, K7150, K7151, K716, K717, K718, K719, K7200, K7201, K7210, K7211, K7290, K7291, K730, K731, K732, K738, K739, K740, K741, K742, K743, K744, K745, K7460, K7469, K750, K751, K752, K753, K754, K7581, K7589, K759, K760, K761, K762, K763, K764, K765, K766, K767, K7681, K7689, K769, K77
Stroke	1 point	History of stroke V12.54, 433.xx-436.xx	G450, G451, G452, G458, G459, G460, G461, G462, I6300, I63011, I63012, I63013, I63019, I6302, I63031, I63032, I63033, I63039, I6309, I6310, I63111, I63112,

HAS-BLED	Point	ICD-9 Codes	ICD-10 Codes
			I63113, I63119, I6312, I63131, I63132, I63133, I63139, I6319, I6320, I63211, I63212, I63213, I63219, I6322, I63231, I63232, I63233, I63239, I6329, I6330, I63311, I63312, I63313, I63319, I63321, I63322, I63323, I63329, I63331, I63332, I63333, I63339, I63341, I63342, I63343, I63349, I6339, I6340, I63411, I63412, I63413, I63419, I63421, I63422, I63423, I63429, I63431, I63432, I63433, I63439, I63441, I63442, I63443, I63449, I6349, I6350, I63511, I63512, I63513, I63519, I63521, I63522, I63523, I63529, I63531, I63532, I63533, I63539, I63541, I63542, I63543, I63549, I6359, I636, I638, I639, I6501, I6502, I6503, I6509, I651, I6521, I6522, I6523, I6529, I658, I659, I6601, I6602, I6603, I6609, I6611, I6612, I6613, I6619, I6621, I6622, I6623, I6629, I663, I668, I669, I67841, I67848, Z8673

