	0D1A8ZH	Bypass Jejunum to Cecum, Via Natural or Artificial Opening Endoscopic
	0D1A8ZK	Bypass Jejunum to Ascending Colon, Via Natural or Artificial Opening Endoscopic
	0D1A8ZL	Bypass Jejunum to Transverse Colon, Via Natural or Artificial Opening Endoscopic
	0D1A8ZM	Bypass Jejunum to Descending Colon, Via Natural or Artificial Opening Endoscopic
	0D1A8ZN	Bypass Jejunum to Sigmoid Colon, Via Natural or Artificial Opening Endoscopic
	0D1A8ZP	Bypass Jejunum to Rectum, Via Natural or Artificial Opening Endoscopic
	0D1B0ZB	Bypass Ileum to Ileum, Open Approach
	0D1B0ZH	Bypass Ileum to Cecum, Open Approach
	0D1B0ZK	Bypass Ileum to Ascending Colon, Open Approach
	0D1B0ZL	Bypass Ileum to Transvers e Colon, Open Approach
	0D1B0ZM	Bypass Ileum to Descending Colon, Open Approach
	0D1B4ZN	Bypass Ileum to Sigmoid Colon, Percutaneous Endoscopic Approach
	0D1B4ZP	Bypass Ileum to Rectum, Percutaneous Endoscopic Approach
	0D1B4ZQ	Bypass Ileum to Anus, Percutaneous Endoscopic Approach
	0D1B8ZB	Bypass Ileum to Ileum, Via Natural or Artificial Opening Endoscopic
	0D1B8ZH	Bypass Ileum to Cecum, Vi a Natural or Artificial Opening Endoscopic

Type	Codes	Description
	0D1B8ZK	Bypass Ileum to Ascending Colon, Via Natural or Artificial Opening Endoscopic
	0D1B8ZL	Bypass Ileum to Transverse Colon, Via Natural or Artificial Opening Endoscopic
	0D1B8ZM	Bypass Ileum to Descending Colon, Via Natural or Artificial Opening Endoscopic
	0D1B8ZN	Bypass Ileum to Sigmoid Colon, Via Natural or Artificial Opening Endoscopic
	0D1B8ZP	Bypass Ileum to Rectum, Via Natural or Artificial Opening Endoscopic
	0D1B8ZQ	Bypass Ileum to Anus, Via Natural or Artificial Opening Endoscopic

Table 10. Charlson Comorbidity Index Score Calculation

Condition	ICD-9 Code(s)	ICD-10 Code(s)	Point
Myocardial Infarction	410.xx; 412.xx	I21, I22, I252	1
Congestive Heart Failure	428.xx	I43, I50, I099, I110, I130, I132, I255, I420, I425, I426, I427, I428, I429, P290	1
Peripheral vascular disease	441.xx; 443.9x; 785.4x; v43.4x, procedure : 38.48	I70, I71, I731, I738, I739, I771, I790, I792, K551, K558, K559, Z958, Z959	1
Cerebrovascular disease	430.xx-438.99 Modified to remove 430.xx-432.xx	G45, G46, I60, I61, I62, I63, I64, I65, I66, I67, I68, I69, H340	1
Dementia	290.xx	F00, F01, F02, F03, G30, F051, G311	1
Chronic obstructive pulmonary disease	490.xx-496.99; 500.xx-505.99; 506.4x	J40, J41, J42, J43, J44, J45, J46, J47, J60, J61, J62, J63, J64, J65, J66, J67, I278, I279, J684, J701, J703	1

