Rheumatologic disease	710.0x-710.19; 710.4x-; 714.0x-714.29; 714.81; 725.xx	M05, M32, M33, M34, M06, M315, M351, M353, M360	1
Peptic ulcer disease	531.0x-531.79; 532.4x-532.79; 533.4x-533.79; 534.0x-534.79; 531.9x; 532.9x; 533.9x; 534.9x Modified to remove: 531.00, 531.01, 531.20, 531.21, 531.40, 531.41, 531.60, 531.61 532.40, 532.41, 532.60, 532.61 533.40, 533.41, 533.60, 533.61, 534.00, 534.01, 534.20, 534.21, 534.40, 534.41, 534.60, 534.61	K25, K26, K27, K28	1

Condition	ICD-9 Code(s)	ICD-10 Code(s)	Point
Mild liver disease	571.2x; 571.4x-571.69	B18, K73, K74, K700, K701, K702, K703, K709, K717, K713, K714, K715, K760, K762, K763, K764, K768, K769, Z944	1
Diabetes (mild to moderate)	250.0x-250.39, 250.7x	E100, E101, E106, E108, E109, E110, E111, E116, E118, E119, E120, E121, E126, E128, E129, E130, E131, E136, E138, E139, E140, E141, E146, E148, E149	1
Diabetes + complications	250.4x-250.69	E102, E103, E104, E105, E107, E112, E113, E114, E115, E117, E122, E123, E124, E125, E127, E132, E133, E134, E135, E137, E142, E143, E144, E145, E147	2
Hemiplegia or paraplegia	342.xx; 344.1x	G81, G82, G041, G114, G801, G802, G830, G831, G832, G833, G834, G839	2
Renal disease	582.xx; 583.0x-583.79; 585.xx-586.99; 588.xx	N18, N19, N052, N053, N054, N055, N056, N057, N250, I120, I131, N032, N033, N034, N035, N036, N037, Z490, Z491, Z492, Z940, Z992	2
Any malignancy, including lymphoma and leukemia	140.xx-172.99; 174.xx-195.99; 200.xx-208.99	C00, C01, C02, C03, C04, C05, C06, C07, C08, C09, C10, C11, C12, C13, C14, C15, C16, C17, C18, C19, C20, C21, C22, C23, C24, C25, C26, C30, C31, C32, C33, C34, C37, C38, C39, C40, C41, C43, C45, C46, C47, C48, C49, C50, C51, C52, C53, C54, C55, C56, C57, C58, C60, C61, C62, C63, C64, C65, C66, C67, C68, C69, C70, C71, C72, C73, C74, C75, C76, C81, C82, C83, C84, C85, C88, C90, C91, C92, C93, C94, C95, C96, C97	2
Moderate/severe liver disease	456.0x-456.29; 572.2x-572.89 Modified to remove: 456.0x, 456.20	K704, K711, K721, K729, K765, K766, K767, I850, I859, I864, I982	3
Metastatic solid tumor	196.xx-199.99	C77, C78, C79, C80	6
AIDS	042.xx-044.99	B20, B21, B22, B24	6

Table 11. Baseline Comorbidities

Covariates	ICD-9-CM/CPT/HCPCS Codes	ICD-10-CM Codes
History Stroke/SE	Same as the outcome stroke/SE (Table 12)	Same as the outcome stroke/SE (Table 12)
History of Bleeding	Same as the outcome major bleeding (Table 12)	Same as the outcome major bleeding (Table 12)

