Transient ischemic attack (TIA)	435.x	G458, G459, Z8673
Coronary artery disease	410.xx-414.xx	I200, I201, I208, I209, I2101, I2102, I2109, I2111, I2119, I2121, I2129, I213, I214, I220, I221, I222, I228, I229, I240, I241, I248, I249, I2510, I25110, I25111, I25118, I25119, I252, I253, I2541, I2542, I255, I256, I25700, I25701, I25708, I25709, I25710, I25711, I25718, I25719, I25720, I25721, I25728, I25729, I25730, I25731, I25738, I25739, I25750, I25751, I25758, I25759, I25760, I25761, I25768, I25769, I25790, I25791, I25798, I25799, I25810, I25811, I25812, I2582, I2583, I2584, I2589, I259
Anemia and coagulation defects	280.xx-286.xx	D50-D53, D55-D59, D60-D69,

Table 12. Clinical Outcomes

Outcome Variables		ICD-9-CM/Procedure Codes	ICD-10-CM Codes/Procedure Codes
Stoke/ SE	Hemorrhagic Stroke	430.xx-432.xx Cases will be excluded if traumatic brain injury (ICD-9: 800-804, 850-854) was present during hospitalization.	I6000, I6001, I6002, I6010, I6011, I6012, I602, I6030, I6031, I6032, I604, I6050, I6051, I6052, I606, I607, I608, I609, I610, I611, I612, I613, I614, I615, I616, I618, I619; Cases will be excluded according to Table 12.
	Ischemic Stroke	433.x1, 434.x1, 436	I6300, I63011, I63012, I63013, I63019, I6302, I63031, I63032, I63033, I63039, I6309, I6310, I63111, I63112, I63113, I63119, I6312, I63131, I63132, I63133, I63139, I6319, I6320, I63211, I63212, I63213, I63219, I6322, I63231, I63232, I63233, I63239, I6329, I6330, I63311, I63312, I63313, I63319, I63321, I63322, I63323, I63329, I63331, I63332, I63333, I63339, I63341, I63342, I63343, I63349, I6339, I6340, I63411, I63412, I63413, I63419, I63421, I63422, I63423, I63429, I63431, I63432, I63433, I63439, I63441, I63442, I63443, I63449, I6349, I6350, I63511, I63512, I63513, I63519, I63521, I63522, I63523, I63529, I63531, I63532, I63533, I63539, I63541, I63542, I63543, I63549, I6359, I636, I638, I639, I6789
	Systemic	444.x, 445.x	I7401, I7409, I7410, I7411, I7419, I742, I743,

Outcome Variables		ICD-9-CM/Procedure Codes	ICD-10-CM Codes/Procedure Codes
	Embolism		I744, I745, I748, I749, I75011, I75012, I75013, I75019, I75021, I75022, I75023, I75029, I7581, I7589

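### In Tables 5, 6 and 10 the ICD-9 and ICD-10 columns define different conditions, so a patient who qualifies only through an affected code scores differently by coding system

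*Combined protocol and SAP*

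**What the plan says.** Section 9.1.1 sets one window: "The study period will range from January 1, 2013 through December 31, 2017". The Appendix gives paired ICD-9 and ICD-10 lists for it, and Table 1 (Section 9.3) makes CHADS2, CHA2DS2-VASc, HAS-BLED and Charlson baseline variables.

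- **Stroke item, 2 points.** Table 5 uses ICD-9 "V12.54, 433-436", and Table 6 uses the same codes under a label beginning "Stroke (non-hemorrhagic only & transient ischemic attack". Both ICD-10 lists run through I63, I65 and I66 and stop at I669.
- **The same ICD-9 codes elsewhere.** In Table 7 (HAS-BLED) the ICD-10 list opens with "G450, G451, G452, G458, G459, G460, G461, G462" and ends with Z8673. Table 11 pairs ICD-9 435.x, labelled TIA, with "G458, G459, Z8673".
- **Charlson, Table 10.** The ICD-9 cerebrovascular entry carries the note "Modified to remove 430.xx-432.xx". The peptic ulcer entry has a similar note for haemorrhagic ulcer codes, and the moderate/severe liver entry says "Modified to remove: 456.0x, 456.20". The ICD-10 column has no such note. It lists I60–I62, the whole of K25–K28, and I850.
- **Vascular item, Table 6, 1 point.** The label covers MI, peripheral arterial disease and aortic plaque. ICD-9 is 410, 412, 440–443, 444.2x and 445.0x. ICD-10 also has I200, I240–I249, I25110, seven I257x0 codes and I670.

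**The concern.** A score should mean the same thing for every patient in a table. Here the two columns of one row admit different conditions, so the same history can earn different points according to the coding system in force during the six-month baseline. That window makes the history codes important: a stroke or TIA before it may be visible only through such a code, and this is a code type missing from the ICD-10 stroke lists.

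Aim 1, a primary objective in Section 8.1.1, describes clinical characteristics, and the tables are compared by anticoagulant. If the apixaban and warfarin cohorts differ in how many patients were coded in ICD-10, part of any difference in mean score would come from the code lists. Any model that used these scores would carry the same error.

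**Working it through.** The plan states no figure to reproduce. The check sets the columns side by side, using the plan's own Tables 7, 11 and 12 as the key.

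**Code coverage**

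- Stroke item: of Table 11's 3 ICD-10 TIA codes, 0 fall in the Table 5 and 6 lists. Of the 11 ICD-10 codes that Table 7 carries beyond I63/I65/I66 (eight G45/G46 codes, I67841, I67848, Z8673), 0 do.
- Charlson ulcer row: Table 12 lists 16 haemorrhagic ulcer codes (K250, K252, K254, K256 and the same endings for K26–K28). All 16 fall inside Table 10's K25–K28.
- Charlson cerebrovascular row: I60–I62 remain in ICD-10, and Table 12 classes them as intracranial haemorrhage.
- Charlson liver row: I850 contains I8501, which Table 12 classes as gastrointestinal bleeding. On the ICD-9 side, taking 456.0x and 456.20 out of 456.0x–456.29 leaves 456.1x and 456.21, so varices not classed as bleeding still score.
- Vascular item: 14 ICD-10 codes lie outside Table 11's MI list. Table 11 puts 13 of them under coronary artery disease (ICD-9 410–414, of which the vascular item takes only 410 and 412). The other is I670; Table 10 counts I67 as cerebrovascular.

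**Points for the same history, when nothing else in that row is coded**

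| Only evidence in the row | Score | ICD-9 | ICD-10 |
|---|---|---|---|
| TIA or stroke/TIA history | CHADS2 | 2 | 0 |
| TIA or stroke/TIA history | CHA2DS2-VASc | 2 | 0 |
| TIA or stroke/TIA history | HAS-BLED | 1 | 1 |
| Haemorrhagic stroke | Charlson | 0 | 1 |
| Bleeding ulcer | Charlson | 0 | 1 |
| Bleeding varices (I8501) | Charlson | 0 | 3 |
| Non-MI coronary code in the Table 6 list | CHA2DS2-VASc | 0 | 1 |

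**Size.** Let *a* be the share of patients whose only stroke-item evidence is a TIA or history code. The documents do not give *a*; 2–15% is an assumption.

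- CHADS2 shift in ICD-10 patients = −2*a*: −2 × 0.02 = −0.04 to −2 × 0.15 = −0.30 points.
- Artefact between cohorts = 2*a* × *d*, where *d* is the difference in ICD-10 share between cohorts (assumed 10–40 percentage points): 0.04 × 0.10 = 0.004 to 0.30 × 0.40 = 0.12 points.
- Standardized difference at an assumed SD of 1.2–1.7: 0.004 / 1.7 = 0.002 to 0.12 / 1.2 = 0.10.
- CHA2DS2-VASc: with *b* the share who gain the vascular point only through the extra ICD-10 codes, the net shift is −2*a* + *b*. It is zero when *b* = 2*a*, for example *a* = 5% and *b* = 10%. Without *b*, the sign is unknown.

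**The case against.** The strongest case against is about reach.

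- A reader might infer that scores are wrong for everyone coded in ICD-10. They are not: a TIA patient who also has any I63, I65 or I66 code still gets 2 points.
- A reader might infer that the propensity model is contaminated. No model names CHADS2 or CHA2DS2-VASc. Section 9.7.1 leaves the IPTW covariates to clinical rationale. Charlson appears only in the matching sensitivity analysis (Section 9.7.2), in a list of variables that may be used: "age, geographic region, Charlson comorbidity index score, comorbidities, and other clinical characteristics". The final choice there is still open.
- Stroke history, bleeding history and TIA are separate baseline flags, index year is a Table 1 variable, and variables left unbalanced after weighting enter the Cox model. The artefact between cohorts computed above stays within the plan's 10% balance limit except at the most extreme assumptions, where it just reaches it.
- Section 9.8 provides for clinical review of the coding strategy.

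Most of this stands, and it limits the point to the scores themselves. Two parts stand only in part. The separate flags are not a full substitute: the stroke/SE history flag copies Table 12, which has neither V12.54 nor Z8673, and the TIA flag is 435.x in ICD-9 but gains Z8673 in ICD-10, so it shifts the other way. Index year is not named as a covariate in either propensity model. The planned coding review does not itself change the lists.

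Nor can the mismatch be read as a deliberate choice. The Table 6 label says TIA counts, and the Charlson removals are stated as modifications but made in one column. Table 5's label says only stroke, yet its ICD-9 list includes 435.

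**Conclusion.** The lists are wrong as written. Followed exactly, they give the same history different points by coding system in scores reported under a primary aim. Only patients who qualify solely through an affected code are mis-scored.

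The firm consequence is for the CHADS2, CHA2DS2-VASc and Charlson rows of the Aim 1 tables, and for any model that uses those scores. CHADS2 is too low in ICD-10 for affected patients, by 0.04–0.30 points on average if 2–15% are affected. The bleeding codes make Charlson too high, by 1 or 3 points per affected patient and row. It is tempting to read CHA2DS2-VASc as systematically too low, but the vascular item errs upward, so its net direction is not established. An effect on the hazard ratios of Aims 2 and 3 is not shown and is probably small.

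The conclusion assumes that both coding systems occur within 2013–2017. The documents give no changeover date, but the paired lists for one study period imply it. The correction should be made before the descriptive tables are run.

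**What to change.** 1. **Tables 5 and 6, stroke item, ICD-10.** Add the TIA and history codes that Table 7 pairs with the same ICD-9 list: G450–G452, G458, G459, G460–G462 and Z8673. Decide explicitly on I67841 and I67848, which Table 7 also carries. Reconcile the result with Table 11's shorter TIA list.
2. **Table 10, ICD-10.** Apply the stated bleeding removals using the Table 12 codes: drop I60–I62, the 16 haemorrhagic codes within K25–K28, and I8501. Do not delete I850 as a whole, because the ICD-9 column keeps non-bleeding varices and a new mismatch would follow.
3. **Table 6, vascular item.** Align the ICD-10 list with the row label and the ICD-9 list.
4. **Check.** Tabulate each item of each score by coding era and look for steps at the changeover.

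The cost is a code-list edit and a rerun of the score programs; no new data are needed. The corrected scores will not match any feasibility tables run on the old lists.
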